14.1.1.2. Serious Adverse Event

An AE is considered “serious” if, in the view of either the Investigator or Sponsor, it results in any of the following outcomes:

- Death
- Is immediately life-threatening
- Requires in-patient hospitalization or prolongation of existing hospitalization
- Results in persistent or significant disability or incapacity
- Results in a congenital abnormality or birth defect

- Is an important medical event that may jeopardize the subject or may require medical intervention to prevent one of the outcomes listed above. Examples of such events are intensive treatment in an emergency room or at home for allergic bronchospasm; blood dyscrasias or convulsions that do not result in hospitalization; or development of drug dependency or drug abuse. Any malignancy is to be reported as an SAE.

Events **not** considered to be SAEs are hospitalizations for:

- Routine monitoring of the studied indication and not associated with any deterioration in condition or AE
- Elective treatment for a pre-existing condition that did not worsen
- Respite care or observation when there is no AE associated with the hospitalization

14.1.1.3. Treatment-Emergent Adverse Events

A TEAE is any event not present before the initiation of the investigational product in this study or any event already present, which worsens in either severity or frequency following exposure to the investigational product in this study.

14.1.1.4. Suspected Unexpected Serious Adverse Reactions

A suspected unexpected serious adverse reaction (SUSAR) is defined as a suspected adverse reaction which is assessed as serious, causally related to the investigational medicinal product, and unexpected per the reference safety information in the Investigator's Brochure.

SUSARs are subject to expedited reporting. The Sponsor shall ensure that all relevant information about SUSARs that are fatal or life-threatening is recorded and reported as soon as possible to the relevant competent authorities (either directly or through the EudraVigilance Clinical Trials Module, as applicable), and to the Ethics Committees, no later than 7 days after knowledge by the Sponsor of such a case. Relevant follow-up information is subsequently communicated within an additional 8 days, unless required differently by local laws and regulations.

All other SUSARs shall be reported to the competent authorities concerned (either directly or through the EudraVigilance Clinical Trials Module) and to the Ethics Committees concerned, within a maximum of fifteen days of first knowledge by the Sponsor.

The Sponsor shall also inform all participating Investigators, as applicable to the local regulations.

14.1.2. Relationship to Treatment Regimen

The Investigator will document her/his medical opinion on the relationship of the AE to treatment with the investigational product using the criteria outlined in [Table 8](#). An AE for which there is a "reasonable possibility" that the investigational product caused the AE is otherwise referred to as suspected adverse reaction (SAR). "Reasonable possibility" means that there is evidence to suggest a causal relationship between the investigational product and the AE.

If the relationship between the AE/SAE and the investigational product is determined to be “definite,” “probable,” or “possible,” the event will be considered to be related to the investigational product for the purposes of expedited regulatory reporting.

Table 8: Relationship of Adverse Events to Treatment Regimen

Relationship	Description
Definite	A reaction that follows a reasonable temporal sequence from administration of the investigational product or in which the investigational product level has been established in body fluids or tissue, that follows a known or expected response pattern to the suspected investigational product, and that is confirmed by improvement on stopping or reducing the dosage of the investigational product and reappearance of the reaction on repeated exposure
Probable	A reaction that follows a reasonable temporal sequence from administration of the investigational product, that follows a known or expected response pattern to the suspected investigational product, that is confirmed by stopping or reducing the dosage of the investigational product, and that could not be reasonably explained by the known characteristics of the subject’s clinical state
Possible	A reaction that follows a reasonable temporal sequence from administration of the investigational product and that follows a known or expected response pattern to the suspected investigational product but that could readily be produced by a number of other factors
Unlikely	A reaction that does not follow a reasonable temporal sequence from administration of the investigational product, that does not follow a known or suspected response pattern to the suspected investigational product, and that could reasonably be explained by known characteristics of the subject’s clinical state
Not Related	Any event that does not meet the above criteria

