8.4.1.1. Severe and Related Adverse Events

If a subject experiences an AE that is \geq Grade 3 in severity using criteria outlined in [Section 14.1.3](#) and is considered possibly, probably, or definitely related to the investigational product, the investigational product must be discontinued. However, subjects should be encouraged to continue study visits, despite stopping investigational product, for continued collection of safety data but may withdraw consent at any time.

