10.2.3. TEAE Analyses

All AE summaries will be restricted to TEAEs. Summaries that are displayed by SOC and PT will be ordered by descending order of incidence of system organ class and preferred term within each system organ class. Summaries of the following types will be presented:

- Overall summary of TEAEs
- Subject incidence of TEAEs and the total number of entries by MedDRA SOC and PT.
- Subject incidence of TEAEs by MedDRA SOC, PT, and highest severity. At each level of subject summarization, a subject is classified according to the highest

severity if the subject reported 1 or more events. AEs with missing severity will be considered severe for this summary.

- Subject incidence of TEAEs by MedDRA SOC, PT, and closest relationship to investigational product (Related/Not Related). Related AEs are those with relationships reported as “Definite,” “Probable,” or “Possible,” and unrelated AEs are those with relationships reported as “Unlikely” or “Not Related.” At each level of subject summarization, a subject is classified according to the closest relationship if the subject reported 1 or more events. AEs with a missing relationship will be considered related for this summary.
- Subject incidence of serious TEAEs and the total number of entries by MedDRA SOC and PT.
- Subject incidence of TEAEs leading to investigational product withdrawal or study discontinuation by MedDRA SOC and PT. This is a subset of the AEs where Action Taken with Study Treatment is checked as “Drug Withdrawn” or where “Subject Discontinued from Study” is checked.

The following listings will be presented by subject:

- All adverse events
- Serious adverse events (a subset of the AEs where serious is marked as “Yes”).
- Severe adverse events (a subset of AEs where severity is marked as “Severe”).
- Related adverse events (a subset of the AEs where relationship marked as “Definite,” “Probable,” or “Possible”).
- Adverse events leading to Study Drug Withdrawal or Study Discontinuation (a subset of the AEs where Action Taken with Study Treatment is checked as “Drug Withdrawn” or where “Subject Discontinued from Study” is checked).
- Adverse events leading to death.

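### Table 8 makes an already recognised reaction pattern a condition of every related rating, so an investigator who applies it as written cannot rate a new type of reaction as related

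*Protocol*

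**What the plan says.** Protocol 14.1.2 asks the investigator for a medical opinion on causality using the Table 8 criteria. The three categories that count as related all carry the same condition:

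- Definite requires a reaction "that follows a known or expected response pattern to the suspected investigational product, and that is confirmed by improvement on stopping" or dose reduction, and by reappearance on re-exposure.
- Probable requires one "that follows a known or expected response pattern to the suspected investigational product, that is confirmed by stopping or reducing the dosage", with no reasonable explanation in the subject's clinical state.
- Possible requires reasonable timing and has the words "and that follows a known or expected response pattern to the suspected investigational product but that could readily be produced by a number"; the row ends by naming alternative causes.

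Unlikely needs three things together: no reasonable timing, no known or suspected pattern, and an explanation in the clinical state. Not Related is the residual: "Any event that does not meet the above criteria".

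The text above the table sets a different standard. A suspected adverse reaction needs a reasonable possibility, which "means that there is evidence to suggest a causal relationship between the investigational product and the AE". That sentence has no pattern condition. The text then makes Definite, Probable and Possible the related group for expedited reporting.

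Section 14.1.1.4 defines a SUSAR as serious, "causally related to the investigational medicinal product, and unexpected per the reference safety information". Section 14.1.4.2 has both the investigator and the sponsor assess the causality of SAEs. SAP 10.2.3 follows the Table 8 split: "Related AEs are those with relationships reported as" Definite, Probable or Possible, while Unlikely and Not Related are tabulated as unrelated.

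**The concern.** The primary objective is the long-term safety and tolerability of a new fixed-dose combination over up to 60 months. Protocol 5.4.3 summarises combination safety from one Phase 1 study and the first 6 months of two Phase 2 studies. Section 5.6.3 says that the overall bezafibrate safety profile comes from a different population and indication. Reactions not yet recognised are therefore among the things this study should find, and Table 8 makes prior recognition a condition of calling an event related.

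The investigator's rating feeds four things:

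- the related group for expedited reporting (14.1.2);
- the rule in 8.4.1.1 for events of Grade 3 or higher "considered possibly, probably, or definitely related to the investigational product, the investigational product must be discontinued";
- follow-up of related events still ongoing at the final visit (14.1.9);
- the related-TEAE summary and listing (SAP 10.2.3).

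The error runs one way. SAP 10.2.3 counts an event with a missing relationship as related, yet a new reaction that recurs on re-exposure would be counted as unrelated.

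**Working it through.** The plan gives no figure to reproduce; the check is whether the table's rows can classify a new reaction as related.

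**Inputs.** Seven yes/no attributes taken from the rows of Table 8: T reasonable timing; L drug level established in fluid or tissue; K recognised pattern; D improvement on stopping or reducing; R reappearance on re-exposure; E explained by clinical state; O other factors could readily produce it.

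**Rules as written.**
- Definite = (T or L) and K and D and R
- Probable = T and K and D and not E
- Possible = T and K and O
- Unlikely = not T and not K and E
- Not Related = none of these

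**Count.** There are 2^7 = 128 profiles, of which 64 have K = no.
- Definite, Probable and Possible all need K, so 0 of the 64 are related.
- Unlikely needs T = no and E = yes: 64 × 1/2 × 1/2 = 16.
- Not Related takes the rest: 64 − 16 = 48. These are all 32 profiles with reasonable timing, plus the 16 with neither timing nor an explanation in the clinical state.

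**One case.** Take T, L, D and R = yes, E and O = no. With K = yes the event meets Definite (and Probable). With K = no it is Not Related. Nothing else about the event differs.

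**Effect of the pattern condition alone.** Drop K from every row, as an illustration and not as proposed wording, assign each profile to the highest category it meets, and reclassify the same 64:
- Definite: 3 combinations of (T or L) × 4 of (E, O), with D and R = yes: 12.
- Probable and not already Definite: T and D = yes, R and E = no, × 4 of (L, O): 4.
- Possible and not already above: 16 with T and O = yes, less 4 Definite and 2 Probable: 10.
- Unlikely: 16 less 2 now Definite: 14.
- Not Related: 64 − 12 − 4 − 10 − 14 = 24.

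Related profiles go from 0 to 12 + 4 + 10 = 26 of 64.

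**Against the text above the table.** Positive dechallenge and rechallenge is evidence suggesting causality. The same section therefore makes the event in the case above a suspected adverse reaction by its prose and Not Related by its table.

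**The residual category.** Consider an event with reasonable timing and a recognised pattern, no confirmation on stopping (a fatal event, for instance) and no other ready cause. It misses Definite and Probable for want of D, Possible for want of O, and Unlikely because T and K hold. It too falls to Not Related, so the catch-all is a weakness apart from the pattern condition.

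**The case against.** Three stronger readings are tempting, and the documents do not support them.

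**A reader might infer that the SUSAR definition can hardly be met.** It can. Section 14.1.1.4 does not refer to Table 8. Under 14.1.4.2 the sponsor assesses causality in addition to the investigator, and nothing binds that assessment to the table. The two tests also differ: a reaction may fit known pharmacology or class effects, and so pass Table 8, yet be absent from the reference safety information.

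**A reader might infer that everything without a recognised pattern becomes Not Related.** Some of it becomes Unlikely, although the SAP treats the two alike.

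**A reader might infer that new reactions would go unseen.** They would not:
- All SAEs reach the sponsor within 24 hours whatever their rating (14.1.4.2).
- The DMC reviews narratives of interval SAEs and a cumulative list of all SAEs (15.9).
- Potential hepatic and renal events are adjudicated (14.3).
- Follow-up under 14.1.9 also covers events of other clinical significance.
- Section 8.4.2 allows discontinuation for events judged clinically important.
- Overall, serious and severity summaries in the SAP do not depend on the rating.

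It is also fair to say that the protocol asks for a medical opinion, and that investigators may use judgment instead of treating the rows as strict logic.

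All of this limits the harm but does not remove the contradiction. Section 14.1.4.2 gives no criteria for the sponsor's assessment and concerns SAEs only. The documents provide no second causality assessment for a non-serious new reaction. Relying on investigators to depart from the stated criteria invites inconsistent ratings across about 60 sites.

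**Conclusion.** The point holds for the investigator's rating. Applied as written, Table 8 gives no related rating to any of the 64 profiles without a recognised pattern, whatever the timing, dechallenge or rechallenge evidence. It thereby contradicts the reasonable-possibility standard of its own section and biases the related-TEAE table and listing downward. For new types of serious reaction, SUSAR identification rests on the sponsor's assessment.

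The result assumes that the rows are applied literally and that their conditions are joined as the wording joins them. The Unlikely row speaks of a suspected pattern where the others speak of an expected one. The count treats these as one attribute; separating them could move events between Unlikely and Not Related but would make none related. The counts are of logical profiles and do not forecast how many events will be misrated. That number cannot be known without the data and the eCRF completion guidelines.

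**What to change.** Reconcile Table 8 with the reasonable-possibility sentence in 14.1.2, and with 14.1.1.4 and 14.1.4.2, so that a recognised pattern supports a related rating but is not required for it. Define Not Related by positive criteria, such as no plausible temporal relationship or a clear other cause, instead of as the residual. State what criteria the sponsor's own assessment uses.

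Carry the wording into the eCRF completion guidelines. Ask sites to re-check only those existing Unlikely or Not Related ratings that were based on the absence of a recognised pattern. A limited re-check also limits the bias that retrospective re-rating in an open-label study can bring.

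The cost is an amendment to wording, guideline text and one targeted review. Somewhat more events will be rated related, and there will be more expedited reports. Because the rating also feeds 8.4.1.1, the sponsor must reconcile that section with the revised table; no stopping rule is proposed here.

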14.1.3. Recording Adverse Event Severity

AEs must be graded for severity (i.e., intensity). A severity category of mild, moderate, or severe, as defined in Table 9, must be entered on the AE eCRF. It should be noted that the term “severe” used to grade intensity is not synonymous with the term “serious.” The assessment of severity is made regardless of investigational product relationship or of the seriousness of the AE.

Table 9: Severity of Adverse Events

Grade	Clinical Description of Severity
1=Mild	Causing no limitation of usual activities; the subject may experience slight discomfort.
2=Moderate	Causing some limitation of usual activities; the subject may experience annoying discomfort.
3=Severe	Causing inability to carry out usual activities; the subject may experience intolerable discomfort or pain.

14.1.3.1. Severity of Pruritus (as an Adverse Event)

To ensure consistency in reporting, pruritus AEs must be graded for severity (i.e., intensity). As pruritus is a subjective symptom, clinical judgment should be used to determine its severity and management, as shown in Table 10. In order to assess the potential improvement in pruritus with treatment, baseline pruritus presence (yes/no) and severity (as shown in Table 10) will be determined.

Table 10: Severity of Pruritus

Pruritus Grade	Clinical Description of Severity for Pruritus and Medical Intervention
1=Mild	Mild or localized; topical intervention indicated
2=Moderate	Intense or widespread; intermittent; skin changes from scratching (e.g., edema, papulation, excoriations, lichenification, oozing/crusts); oral intervention indicated; limiting instrumental activities of daily living
3=Severe	Intense or widespread; constant; limiting self-care activities of daily living or sleep; oral corticosteroid or immunosuppressive therapy indicated

Since pruritus is a subjective symptom and the occurrence and magnitude of which are not readily measured by objective tools, clinical judgment needs to be applied in the management of each subject. Managing OCA-related pruritus may help improve tolerance in those subjects who experience problematic pruritus and may otherwise discontinue from the study prematurely. General guidance for the management of subjects experiencing significant pruritus includes the following:

- Drug holiday: A drug holiday is defined as an Investigator's "prescribed" complete interruption of dosing for 1 or more consecutive days (i.e., nondaily dosing does not constitute a drug holiday). Details of drug holidays and/or nondaily dosing regimens should be recorded in the eCRF. If the drug holiday lasts more than 30 days, the subject should be permanently discontinued from investigational product but requested to continue with study visits until Month 60/EOS.
- Per [Section 8.4.1.1](#), subjects with pruritus \geq Grade 3 in severity and possibly, probably, or definitely related to the investigational product must discontinue investigational product but are encouraged to continue study visits.
- Subjects taking BAS (including cholestyramine and its derivatives, colestipol, colesevelam, or other BAS) or aluminum hydroxide- or smectite-containing antacids should refrain from using these drugs for the management of pruritus during the trial. The use of BAS may alter the interpretation of the effects of BZF on pruritus.
- Other therapies may be tried as deemed clinically appropriate.
- Rifampin should be used with caution in patients with PBC due to the hepatotoxicity concerns as specified in the rifampin USPI.
- Less frequent dosing of investigational product (e.g., on alternate days) may be administered, after which, subjects may return to their original daily dose as soon as tolerated.

14.1.4. Reporting of Adverse Events and Serious Adverse Events

14.1.4.1. Reporting of Adverse Events

AE data will be collected from the time that signed informed consent is obtained until the subject fully completes her/his study participation.

All AEs, whether believed by the Investigator to be related or unrelated to the investigational product, must be documented in the subject's medical records and on the AE eCRF. Each AE is to be evaluated for duration, severity, frequency, seriousness, outcome, other actions taken, and relationship to the investigational product.

In addition, the Investigator should contact the study Medical Monitor upon awareness when any signs or symptoms of hepatic decompensation are observed in any subject.

14.1.4.2. Reporting of Serious Adverse Events

In agreeing to the provisions of this protocol, the Investigator accepts all legal responsibilities for immediate reporting of SAEs to the Sponsor.

All SAEs must be immediately reported (i.e., within 24 hours of awareness) to the Sponsor.

SAEs are reported by entering the SAE data into the study-specific EDC system. Entering the SAE data into the EDC system will automatically notify the Sponsor of the SAE. In the event that the EDC system is inaccessible, an SAE may be reported by:

- Sending an SAE report form via email to: [contact]
- Fax using a paper SAE report form: [name]

If an SAE is initially reported by e-mail or fax, SAEs must also be entered in the EDC system as soon as the EDC system is accessible. At a minimum, the following information should be provided at the time of the initial report:

- Subject number
- Event term
- At least 1 criterion classifying the event as serious
- Name and title of the reporting individual
- Causal relationship to the investigational product

The Investigator will assess whether the event is causally related to the investigational product. The Sponsor will also assess whether the event is causally related to the investigational product, in addition to assessing the overall safety profile of the investigational product. The Sponsor will notify the appropriate regulatory agencies as well as all participating Investigators (where required) of Expedited Safety Reports that occur during the study within the time frames required by each regulatory agency.

Following the initial report, any additional information obtained by the Investigator about the SAE must be reported promptly to the Sponsor in the same manner as described above for the initial SAE report. Any supporting source documentation should be faxed to [contact]

or e-mailed to [contact] as soon as possible. Redacted medical record source documentation will be requested for all SAEs.

The Investigator is responsible for submitting information on Expedited Safety Reports received from the Sponsor to her/his local IRB/IEC, as directed by the local-country requirements. Documentation of the applicable submissions to IRBs/IECs must be retained in the appropriate study file(s). As instructed by the Sponsor, Expedited Safety Reports should be retained in the appropriate investigative site study files, or with the Investigator's Brochure (IB).

